An exploratory endpoint will be the rate of viral respiratory infection, irrespective of whether the infection is symptomatic, to better assess the antiviral effects of RTB101. As an additional exploratory endpoint, healthcare resource utilization will be assessed because an important benefit of decreasing the incidence of clinically symptomatic respiratory illness may be a decrease in healthcare resource utilization by elderly subjects. Since decreasing the incidence of clinically symptomatic respiratory illness may improve the quality of life of elderly subjects, an

additional exploratory endpoint will be health related quality of life in all subjects assessed with the EQ-5D-5L questionnaire. The incidence of clinically symptomatic respiratory illness in subjects with a medical history of asthma or who are ≥ 85 years of age will be assessed as exploratory endpoints because these subpopulations had the greatest reduction on the incidence of laboratory confirmed RTIs after treatment with 10 mg RTB101 once daily as compared with placebo in the previous Phase 2b (RTB-BEZ235-202) trial. The incidence of asthma exacerbations in subjects with a medical history of asthma will also be assessed since RTIs are common causes of asthma exacerbations. Another exploratory endpoint will be the incidence of clinically symptomatic respiratory illness and the incidence of symptomatic respiratory illness associated with laboratory-confirmed pathogen(s) through Week 20 to assess if the efficacy of RTB101 persists for 4 weeks after subjects discontinue study drug. To better understand if the incidence of other types of infections may be reduced, the incidence of UTIs will be assessed. Finally, RNA expression and soluble serum biomarkers and pharmacogenomics (also known as pharmacogenetics) (Note: pharmacogenomics will only be assessed in those subjects who sign a separate consent form to allow collection of a pharmacogenomic (also known as pharmacogenetic) sample) will be assessed as exploratory endpoints to assess the effects of RTB101 on relevant immunologic markers and to potentially assess the impact of mTOR pathway polymorphisms in a pharmacogenomic analysis.

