6.7.2. Laboratory-Confirmed Clinically Symptomatic Respiratory Illness

When a subject reports symptoms of a respiratory illness in which at least one unique respiratory symptom (runny nose, sneezing, stuffy nose, sore throat, hoarseness, or cough) is reported on 2 consecutive entries in their eDiary, the sites will contact the subject and instruct the subject to come to the study site if they are able to within 48 hours for evaluation and to obtain a nasopharyngeal swab. Subjects should only have one nasopharyngeal swab obtained during each episode of a respiratory illness. Please refer to the SOM for more details. Laboratory confirmation of clinically symptomatic respiratory illness will be obtained using three methods:

- The FILMARRAY Respiratory panel polymerase chain reaction (PCR) Assay of nasopharyngeal swabs in all subjects
- Sputum gram stain and culture obtained in subjects with a productive cough that is new or a change from their normal baseline
- RIDT obtained in subjects with influenza-like illness symptoms (such as 1 or more respiratory symptom (cough, sore throat or nasal symptoms) and 1 or more constitutional symptom (such as body aches or feverishness/chills)).

Subjects who are unwilling or unable to come to the study site for an unscheduled visit should have the nasopharyngeal swab (and sputum specimen or RIDT , if indicated) obtained at a home visit by trained personnel. All subjects with influenza-like illness who have influenza detected by RIDT or nasopharyngeal swab PCR should receive anti-influenza treatment per local standard of care, unless contraindicated, and/or other appropriate medical care.

Study drug treatment can be continued in subjects who require antibiotics or anti-influenza treatment for treatment of an RTI.

Laboratory-confirmed clinically symptomatic respiratory illness will be defined programmatically as a symptomatic respiratory illness that meets the prespecified clinical diagnostic criteria outlined in [Section 6.7.1](#) and is associated with a laboratory-confirmed pathogen detected by one or more of the 3 methods described above. Further details will be provided in the SAP.

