6.7.4. Appropriateness of Efficacy Assessments

The primary and secondary efficacy assessments selected for this protocol are appropriate to measure the incidence, severity and duration of clinically symptomatic respiratory illness. Daily reporting of respiratory illness symptoms via an eDiary will help assure that clinically symptomatic respiratory illness events are rapidly captured during the trial. Obtaining laboratory confirmation if you are able to within 48 hours of symptom confirmation when viral detection is likely to be highest using a Food and Drug Administration (FDA)-approved PCR panel assay (FilmArray Respiratory Panel, 510(k) NO: K152579 [Dual track]) that detects 17 viral and 3 bacterial respiratory pathogens will also help increase rates of laboratory-confirmation of clinically symptomatic respiratory illness.

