The percentage of subjects with severe symptoms due to CSRIs beginning at least 3 days after the start of study drug treatment through Week 16 (H_6) will be analyzed in the same manner as the primary efficacy endpoint, as described in [9.3.1 above](#) based on the estimand for the secondary objective corresponding to this secondary endpoint as described in [9.2.2 above](#).

Summary statistics will be presented along with a full data listing by treatment group.

9.4.6. Rate of Clinically Symptomatic Respiratory Illnesses Associated with Specific Laboratory-confirmed Viruses

A comparison of the rate of clinically symptomatic respiratory illnesses associated with specific laboratory-confirmed viruses (coronaviruses, hMPV, HRV/enterovirus, adenovirus, influenza A and B virus, parainfluenza viruses, and RSV) beginning at least 3 days after the start of study drug treatment through Week 16 as assessed by respiratory pathogen PCR of nasopharyngeal swabs and/or RIDTs is not powered to demonstrate a pre-specified treatment effect. This endpoint will be analyzed in the same manner as described in [9.4.2 above](#). However, there will be no formal statistical tests conducted and no p-values will be presented. To demonstrate trends consistent with the primary endpoint for the pre-specified laboratory-confirmed viruses, the estimated rate of the laboratory-confirmed viruses and associated CIs will be presented by treatment arm.

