9.5. Analyses of Exploratory Efficacy Endpoints

9.5.1. Rate of All Laboratory-confirmed Viral Infections with or without Symptoms

The rate of all laboratory-confirmed viral infections with or without symptoms beginning at least 3 days after the start of study drug treatment through Week 16 as assessed by respiratory pathogen PCR of nasopharyngeal swabs and/or RIDTs (obtained during episodes of clinically symptomatic respiratory illnesses) and/or respiratory pathogen PCR of mid-turbinate swabs (obtained at required clinical visits even in the absence of symptoms) will be analyzed in the same manner as described in [9.4.2 above](#).

All positive results from specimens (respiratory pathogen PCR of nasopharyngeal swabs or midturbinate swabs and/or RIDT) collected at least 3 days after the start of study drug treatment through Week 16, which may or may not be associated with a CSRI, will count as laboratory-confirmed viral infections (both symptomatic and asymptomatic).

This document is confidential.

Summary statistics will be presented along with a full data listing by treatment group.

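### SAP 9.5.1 counts every positive respiratory pathogen PCR as a viral infection, although the panel named for nasopharyngeal swabs also reports 3 bacterial targets (minor; exploratory endpoint)

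*SAP*

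**What the plan says.** The first sentence of SAP 9.5.1 names the endpoint: "The rate of all laboratory-confirmed viral infections with or without symptoms beginning at least 3 days after the start of study drug treatment". The window closes at Week 16. It is analysed by the negative binomial method of SAP 9.4.2. The next paragraph gives the counting rule. It covers "All positive results from specimens (respiratory pathogen PCR of nasopharyngeal swabs or midturbinate swabs and/or RIDT) collected" from 3 days after the start of study drug through Week 16, whether or not they belong to a CSRI, and says that they "will count as laboratory-confirmed viral infections (both symptomatic and asymptomatic").

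The assay is described in the protocol. Section 6.7.2 lists, as the first method of laboratory confirmation, "The FILMARRAY Respiratory panel polymerase chain reaction (PCR) Assay of nasopharyngeal swabs in all subjects". Section 6.7.4 says that this panel "detects 17 viral and 3 bacterial respiratory pathogens". Neither section names a panel for the mid-turbinate swabs. Table 6-1 schedules those at Baseline and at Weeks 2, 4, 6, 8, 12 and 16.

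The purpose is given in Protocol 3.2: "An exploratory endpoint will be the rate of viral respiratory infection, irrespective of whether the infection is symptomatic", included as a better measure of the drug's antiviral effect.

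**The concern.** The rule and the endpoint that it defines do not agree. The endpoint is viral. The rule admits any positive PCR result, and the named panel can be positive for an organism that is not a virus. SAP 9.4.6, the virus-specific secondary endpoint, avoids the problem by listing its targets: "coronaviruses, hMPV, HRV/enterovirus, adenovirus, influenza A and B virus, parainfluenza viruses, and RSV". SAP 9.5.1 has no such list and no equivalent restriction.

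At stake is what the endpoint measures. If bacterial detections are counted, the result is mislabelled, and it answers the antiviral question less directly than Protocol 3.2 intends. A viral filter added after unblinding would be a post-hoc change to an endpoint definition.

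The point concerns which organisms are counted. How often repeat positives from one infection are counted is a separate matter.

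**Working it through.** **The plan's own figure.** No sample size, power or expected rate is given for this endpoint. The only sample-size figure is 1066 for the primary endpoint (Protocol 9.6, SAP 3.6). It reproduces with the likelihood-ratio chi-square test: 28.2% against 0.70 × 28.2% = 19.74%, two-sided 0.05, gives N = 1066 and power 90.0%. Nothing below depends on it.

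**Step 1: follow the rule for one specimen.** Take a nasopharyngeal swab collected in Week 5 that is positive for one of the 3 bacterial targets and for nothing else.

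- Is it a positive respiratory pathogen PCR of a nasopharyngeal swab? Yes.
- Was it collected in the window? Yes.
- Does SAP 9.5.1 ask which organism was found? No.
- Result: counted as a laboratory-confirmed viral infection.

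This step needs no assumption about the drug.

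**Step 2: which specimens are affected.** For nasopharyngeal swabs the 3 bacterial targets are documented. For mid-turbinate swabs the SAP uses the same general term for the PCR, but no panel or target list is given. Whether Step 1 applies to them is an open question. It matters because they are scheduled at six post-baseline visits regardless of symptoms, whereas nasopharyngeal swabs are triggered by symptoms.

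**Step 3: effect on the rate ratio.** Let b be the bacterial share of counted positives on placebo, RRv the true ratio for viral detections and RRb the ratio for bacterial detections. If the placebo rate is λ, the RTB101 rate is (1 − b)λ·RRv + bλ·RRb. Dividing by λ gives

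RR observed = (1 − b)·RRv + b·RRb.

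The documents give none of b, RRv or RRb, so all values below are assumptions. The 0.70 borrows the 30% relative reduction planned for the primary endpoint, which is a percentage of subjects with CSRI and not a detection rate.

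| RRv | RRb | b = 1% | b = 5% | b = 15% |
|---|---|---|---|---|
| 0.70 | 1.0 | 0.703 | 0.715 | 0.745 |
| 0.70 | 0.70 | 0.700 | 0.700 | 0.700 |
| 0.70 | 1.3 | 0.706 | 0.730 | 0.790 |
| 0.80 | 0.70 | 0.799 | 0.795 | 0.785 |

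For example, in the first row at 5%: 0.95 × 0.70 + 0.05 × 1.0 = 0.715. In the last row at 5%: 0.95 × 0.80 + 0.05 × 0.70 = 0.795.

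**Step 4: after the fix.** Restricting the count to viral targets sets b = 0, so RR observed = RRv in every row.

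**The case against.** The strongest reply is that the intent is plain. The heading and first sentence of SAP 9.5.1, the endpoint list in SAP 4.3 and Protocol Table 2-1 all say viral. Section 9.5.1 also leaves out sputum gram stain and culture, which SAP 9.4.1 includes for the any-pathogen endpoint. A careful programmer could read the second paragraph as settling specimen type, window and symptom status within an endpoint already defined as viral. This stands as evidence of what was meant. It does not remove the operative sentence, which says which results count and says all of them. No other section supplies the filter.

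A reader might go further and infer that the rule necessarily dilutes the rate ratio toward 1. The documents do not support that. Dilution requires RTB101 to act less on bacterial than on viral detections. The antiviral mechanism in Protocol 3.2 makes this plausible, but Protocol 1.1 hopes for fewer infections whichever pathogen is responsible. The second and fourth rows of the table show no shift and a shift away from 1.

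Nor does the panel's make-up bound the effect. 3 of 20 targets is 15%, but a count of assay targets says nothing about the share of positive results. The 15% column is illustrative only.

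It is also fair that the stakes are low. The endpoint is exploratory, SAP 9.4.6 already reports virus-specific rates for symptomatic illness, and the planned swab listings (16.2.6.2.1 and 16.2.6.2.2) could be used to look for bacterial-only positives.

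**Conclusion.** The counting rule is wrong as written: it contradicts the endpoint that it defines. For nasopharyngeal swabs this follows from the text alone. For mid-turbinate swabs it holds only if they use the same panel.

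The numerical consequence is unknown in size and direction. At assumed bacterial shares of 1% to 5%, with a viral ratio of 0.70 and no bacterial effect, the reported ratio moves by 0.003 to 0.015. Under other assumptions it does not move, or moves the opposite way. What remains in every case is misclassification.

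The point is minor. A reader should not infer any threat to the trial's main conclusions: the endpoint is outside the fixed sequence H1 to H9, and the primary endpoint, the control of alpha and the sample size are untouched.

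**What to change.** In SAP 9.5.1, change the opening of the counting sentence to: *All positive results for a viral target (PCR) or influenza (RIDT) from specimens*, and leave the rest as it stands. This wording deliberately keeps results as the counting unit. Switching to specimens positive for at least one virus could also change how a swab with two viruses is counted, which is a different decision. List bacterial-only positives separately, and state in the same place which panel is used for mid-turbinate swabs.

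The cost is one phrase in the SAP and one filter in the program. Organism-level results for nasopharyngeal swabs are already needed for SAP 9.4.6, so no new data are required. The change should be made before unblinding.

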9.5.2. Rate of All-cause Hospitalizations

The rate of all-cause hospitalizations beginning at least 3 days after the start of study drug through Week 16 (**H**₇) will be analyzed in the same manner as described in [9.4.2 above](#).

Summary statistics will be presented along with a full data listing by treatment group.

9.5.3. Rate of Hospitalizations Associated with RTIs

The rate of hospitalizations associated with RTIs beginning at least 3 days after the start of study drug through Week 16 will be analyzed in the same manner as described in [9.4.2 above](#).

Summary statistics will be presented along with a full data listing by treatment group.

9.5.4. Rate of All-cause Emergency Room Visits

The rate of all-cause Emergency Room (ER) visits beginning at least 3 days after the start of study drug through Week 16 will be analyzed in the same manner as described in [9.4.2 above](#).

Summary statistics will be presented along with a full data listing by treatment group.

9.5.5. Rate of Emergency Room Visits with RTIs

The rate of ER visits associated with RTIs beginning at least 3 days after the start of study drug treatment through Week 16 will be analyzed in the same manner as described in [9.4.2 above](#).

Summary statistics will be presented along with a full data listing by treatment group.

9.5.6. Rate of All-cause Urgent Care Clinic Visits for Clinically Symptomatic Respiratory Illness

The rate of all-cause urgent care clinic for clinically symptomatic respiratory illness visits beginning at least 3 days after the start of study drug treatment through Week 16 will be analyzed in the same manner as described in [9.4.2 above](#).

Summary statistics will be presented along with a full data listing by treatment group.

9.5.7. Rate of All-cause Urgent Care Clinic Visits

The rate of all-cause urgent care clinic visits beginning at least 3 days after the start of study drug through Week 16 will be analyzed in the same manner as described in [9.4.2 above](#).

Summary statistics will be presented along with a full data listing by treatment group.

9.5.8. Rate of All-cause Admissions to Skilled Nursing Facilities

The rate of all-cause admissions to skilled nursing facilities beginning at least 3 days after the start of study drug through Week 16 will be analyzed in the same manner as described in [9.4.2 above](#)

Summary statistics will be presented along with a full data listing by treatment group.

This document is confidential.

9.5.9. Hospitalization Length of Stay Associated with RTIs

Total hospitalization length of stay associated with RTIs beginning at least 3 days after the start of study drug treatment through Week 16 will be analyzed as an exploratory endpoint.

Total hospitalization length of stay associated with RTIs will consist of the total duration of hospitalizations associated with RTIs for each subject starting between 3 days after the start of study drug and prior to Week 16. Duration of a hospital stay is defined as (hospital discharge date – hospital admission date) +1.

The analysis will be performed using the Analysis of Covariance model (PROC MIXED) with fixed effects for treatment group, age (continuous covariate), Clinical Frailty Scale score (ordinal covariate), medical history of diabetes mellitus type 2 (Y/N), medical history of asthma (Y/N), medical history of CHF (Y/N), and receipt of current season influenza vaccination (Y/N) as covariates. The least squares (LS) means, differences between LS means, a 95% 2-sided CLs for the difference and the p-values from model effects will be reported for overall treatment to evaluate the treatment effect.

Summary statistics, including Least Squares Mean and standard error for each treatment and the treatment difference will be presented along with a full data listing by treatment group.

9.5.10. Percentage of Subjects with 1 or more Clinically Symptomatic Respiratory Illnesses (with or without an Associated Laboratory-confirmed Pathogen) through Week 20

The percentage of subjects with 1 or more CSRIs (with or without an associated laboratory-confirmed pathogen) beginning at least 3 days after the start of study drug treatment through Week 20 (**H₉**) will be analyzed in the same manner as the primary efficacy analysis as described in [9.3.1 above](#).

Summary statistics will be presented along with a full data listing by treatment group.

9.5.11. Percentage of Subjects with 1 or more Clinically Symptomatic Respiratory Illnesses Associated with ≥ 1 Laboratory-confirmed Pathogen(s) through Week 20

The percentage of subjects with 1 or more CSRIs associated with ≥ 1 laboratory-confirmed pathogen(s) beginning at least 3 days after the start of study drug treatment through Week 20 as assessed by pre-specified clinical diagnostic criteria and respiratory pathogen PCR of nasopharyngeal swabs, sputum gram stain and culture, and/or RIDTs will be analyzed in the same manner as the primary efficacy analysis as described in [9.3.1 above](#). [Section 9.4.1](#) describes which laboratory result will be used to determine if the CSRI is associated with ≥ 1 laboratory-confirmed pathogen.

Summary statistics will be presented along with a full data listing by treatment group.

9.5.12. All-cause Hospitalization Length of Stay

All-cause hospitalization total length of stay beginning at least 3 days after the start of study drug through Week 16 will be analyzed in the same manner described in 9.5.9 above.

Summary statistics will be presented along with a full data listing by treatment group.

This document is confidential.

9.5.13. Change from Baseline in EQ-5D-5L Scores during All Clinically Symptomatic Respiratory Illness Episodes and at Week 16

The change from Baseline in HRQoL as assessed by EQ-5D-5L Visual Analog Scale (VAS) scores during all CSRI episodes beginning at least 3 days after the start of study drug treatment through Week 16 and at Week 16 will be analyzed using a Mixed Model Repeated Measure model (PROC MIXED). The model will include the change from Baseline in EQ-5D-5L (measured each day during a CSRI event and at the Week 16 visit) as the dependent variable and will include patient as a random effect, and fixed effects of treatment group, Baseline EQ-5D-5L, time (study day the measure was taken), and a treatment-by-time interaction.

The Kenward-Roger approximation will be used to adjust the denominator degrees of freedom. An unstructured (general) covariance structure will be assumed initially to model the within-subject errors; however, other covariance structures will be tested and may be used in the final model if a better fit is evident. The least squares (LS) means, differences between LS means, a 95% 2-sided CLs for the difference and the p-values from model effects will be reported for overall treatment to evaluate the treatment effect.

Summary statistics for the VAS and individual items and associated boxplot for VAS will be presented along with a full data listing of EQ-5D-5L data by treatment group.

9.5.14. Percentage of Subjects with One or More Clinically Symptomatic Respiratory Illnesses (with or without an Associated Laboratory-confirmed Pathogen) through Week 16 who are ≥ 85 years of age

The percentage of subjects with one or more CSRI episodes beginning at least 3 days after the start of study drug treatment through Week 16 who are ≥ 85 years of age will be analyzed in the same manner as the primary efficacy analysis as described in [9.3.1 above](#).

Summary statistics will be presented along with a full data listing by treatment group.

9.5.15. Rate of Clinically Symptomatic Respiratory Illnesses (with or without an Associated Laboratory-confirmed Pathogen) through Week 16 in Subjects who are ≥ 85 years of age

The rate of CSRI episodes (with or without an associated laboratory-confirmed pathogen) beginning at least 3 days after the start of study drug treatment through Week 16 in subjects who are ≥ 85 years of age will be analyzed in the same manner as described in [9.4.2 above](#). Summary statistics will be presented along with a full data listing by treatment group.

Summary statistics will be presented along with a full data listing by treatment group.

9.5.16. Percentage of Subjects with One or More Clinically Symptomatic Respiratory Illnesses (with or without an Associated Laboratory-confirmed Pathogen) through Week 16 who have a Medical History of Asthma

The percentage of subjects with one or more CSRI episodes at least 3 days after the start of study drug treatment through Week 16 who have a medical history of asthma will be analyzed in the same manner as the primary efficacy analysis as described in [9.3.1 above](#).

This document is confidential.

Summary statistics will be presented along with a full data listing by treatment group.

- 9.5.17. Rate of Clinically Symptomatic Respiratory Illnesses (with or without an Associated Laboratory-confirmed Pathogen) through Week 16 in Subjects who have a Medical History of Asthma

The rate of CSRI (with or without an associated laboratory-confirmed pathogen) beginning at least 3 days after the start of study drug treatment through Week 16 in subjects who have a medical history of asthma will be analyzed in the same manner as described in [9.4.2 above](#). Summary statistics will be presented along with a full data listing by treatment group.

Summary statistics will be presented along with a full data listing by treatment group.

- 9.5.18. Percentage of Subjects with One or More Clinically Symptomatic Respiratory Illnesses Associated with ≥ 1 Laboratory-confirmed Pathogen(s) through Week 16 who are ≥ 85 years of age

The percentage of subjects with one or more CSRI associated with ≥ 1 laboratory-confirmed pathogen(s) at least 3 days after the start of study drug treatment through Week 16 who are ≥ 85 years of age will be analyzed in the same manner as the primary efficacy analysis as described in [9.3.1 above](#). [Section 9.4.1](#) describes which laboratory result will be used to determine if the CSRI is associated with ≥ 1 laboratory-confirmed pathogen.

Summary statistics will be presented along with a full data listing by treatment group.

- 9.5.19. Percentage of Subjects with One or More Clinically Symptomatic Respiratory Illnesses Associated with ≥ 1 Laboratory-confirmed Pathogen(s) through Week 16 who have a Medical History of Asthma

The percentage of subjects with one or more CSRI associated with ≥ 1 laboratory-confirmed pathogen(s) at least 3 days after the start of study drug treatment through Week 16 who have a medical history of asthma will be analyzed in the same manner as the primary efficacy analysis as described in [9.3.1 above](#). Summary statistics will be presented along with a full data listing by treatment group. [Section 9.4.1](#) describes which laboratory result will be used to determine if the CSRI is associated with ≥ 1 laboratory-confirmed pathogen.

- 9.5.20. Rate of Clinically Symptomatic Respiratory Illnesses Associated with ≥ 1 Laboratory-confirmed Pathogen(s) through Week 16 in Subjects who are ≥ 85 years of age

The rate of CSRI associated with ≥ 1 laboratory-confirmed pathogen(s) in subjects who are ≥ 85 years of age beginning at least 3 days after the start of study drug treatment through Week 16 will be analyzed in the same manner as described in [9.4.2 above](#). [Section 9.4.1](#) describes which laboratory result will be used to determine if the CSRI is associated with ≥ 1 laboratory-confirmed pathogen.

Summary statistics will be presented along with a full data listing by treatment group.

- 9.5.21. Rate of Clinically Symptomatic Respiratory Illnesses Associated with ≥ 1 Laboratory-confirmed Pathogen(s) through Week 16 in Subjects with a Medical History of Asthma

The rate of CSRI associated with ≥ 1 laboratory-confirmed pathogen(s) in subjects with a medical history of asthma beginning at least 3 days after the start of study drug treatment through Week 16 will be

This document is confidential.

analyzed in the same manner as described in [9.4.2 above](#). [Section 9.4.1](#) describes which laboratory result will be used to determine if the CSRI is associated with ≥ 1 laboratory-confirmed pathogen.

Summary statistics will be presented along with a full data listing by treatment group.

9.5.22. Rate of Asthma Exacerbations through Week 16 in Subjects with a Medical History of Asthma

The rate of asthma exacerbations, defined as deterioration of asthma symptoms that requires treatment with systemic steroids, beginning at least 3 days after the start of study drug treatment through Week 16 in subjects with a medical history of asthma will be analyzed in the same manner as described in [9.4.2 above](#).

Summary statistics will be presented along with a full data listing by treatment group.

9.5.23. Percentage of Subjects with 1 or more Asthma Exacerbation through Week 16 in Subjects with a Medical History of Asthma

The percentage of subjects with 1 or more asthma exacerbation defined as deterioration of asthma symptoms that requires treatment with systemic steroids beginning at least 3 days after the start of study drug treatment through Week 16 in subjects with a medical history of asthma will be analyzed in the same manner as the primary efficacy analysis as described in [9.3.1 above](#).

Summary statistics will be presented along with a full data listing by treatment group.

9.5.24. Change from Baseline to Weeks 4 and 16 in Biomarkers in Whole Blood

Blood samples will be obtained for exploratory biomarker analyses, including RNA expression in whole blood and soluble biomarkers in serum, in all subjects at the Baseline and Week 16 visit, and for subjects in the pharmacokinetic analysis subset (approximately 400 subjects) at the Week 4 or Week 6 visit (4 hours after study drug administration). The RNA expression to be measured may include:

- IFNG
- IFI44L
- IFIT5
- IFIH1
- MSR1
- IFIT1
- IFIT2
- HERC5
- MX1
- IFITM3
- OAS2
- IFIT3
- RSAD2
- ISG15
- IFI27
- IFI6
- STAT2

This document is confidential.

- STAT1
- SOCS3
- IRF7
- OASL
- OAS3

The list may be changed or expanded further, as it is recognized that more relevant or novel biomarkers may be discovered during the conduct of the study.

Summary statistics of the biomarkers by clinical visit and their associated change from baseline values will be presented along with a full data listing by treatment group.

